### 7.9.2 Secondary Performance Endpoints

- Successful access, delivery of implant, and retrieval of the delivery system

## Hypothesis/Decision Criteria:

No specific hypotheses or pass/fail criteria have been set. The analysis will be descriptive and no statistical hypothesis tests are planned.

## Endpoint Definition/Parameters to Be Estimated:

This endpoint is defined using variables on the procedure CRF.

- Successful access is "Yes" if "TMVR delivery catheter insertion time" is not blank.
- Successful delivery of implant is "Yes" if "Was the TMVR implanted?" is answered "Yes" and "Conversion to open surgical MV replacement" is answered "No".
- Successful retrieval delivery system is "Yes" if "Delivery catheter removal time" is not blank.

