- Other systemic effects or symptoms (e.g., abnormal lab values, electrolyte imbalance, fever, hyperthermia, hypotension, hypertension, syncope, nausea, vomiting, edema, deep vein thrombosis, pleural effusion, lymphatic complications, urinary tract infection, multi-system organ failure, gastrointestinal bleeding, ischemia or infarction)
- Valve implant dysfunction (e.g., fracture, bending, under-expansion, suture breaks, calcification, pannus, thrombus, inflammation, stenosis, leaflet wear, tear, prolapse, retraction, poor valve coaptation, leaks, regurgitation, mal-sizing [prosthesis-patient mismatch])

The risks of the investigational TMVR procedure are similar to the surgical risks listed above; however some may be increased with the TMVR procedure or implant. For example, the risks of cardiac damage may be increased by the TMVR delivery, and the risk of valve implant dysfunction (as compared to surgical replacement valves) has not yet been established.

In addition to the risks listed above, the potential risks associated with the TMVR procedure and the Intrepid TMVR System may include, but are not limited to, the following risks:

- Valve implant detachment, migration, malposition, and/or incorrect sizing
- Reduced ventricular function due to apical incision and sheath insertion
- Ventricular insertion site complications (e.g., bleeding, rupture, septal perforation, aneurysm or pseudoaneurysm)
- Injury to mitral valve apparatus complicating or preventing later surgical repair/replacement
- Left ventricular outflow tract (LVOT) obstruction
- Emergent surgical or transcatheter intervention (for example, coronary artery bypass, heart valve replacement or repair, transcatheter valve explant, percutaneous coronary intervention [PCI], balloon valvuloplasty, transcatheter valve or component retrieval)
- Failure to deliver the bioprosthetic to the intended site
- Failure to retrieve the system components
- Delivery system component(s) embolization
- Delivery system thrombosis
- Prolonged cardiopulmonary bypass
- Prolonged ventilation, anesthesia, and/or procedure time
- Radiation skin burn or tissue reaction

The likelihood of these risks is unknown, as this is the initial introduction of the investigational TMVR system into a human population. However, bench-top testing and animal studies have

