## Data Collection and Analysis Dataset:

Data for this endpoint are collected on the procedure CRF. Data will be summarized on the Attempted Subjects analysis set.

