## Analysis Method:

The proportion of subjects with each of successful access, successful delivery of implant, and successful retrieval of the delivery system and its associated 95% exact confidence interval will be calculated.

- Reduction in MR Grade from baseline (measured by echo through 30 days post-procedure)

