## Endpoint Definition/Parameters to Be Estimated:

This endpoint is defined using variables on the AE and procedure CRFs.

Technical success is measured at exit from the catheterization laboratory and all of the following must be present:

- Absence of procedural mortality (free from death on day 0, which is day of procedure, AE CRF); and
- Successful access, delivery, and retrieval of the delivery system (same definition as secondary endpoint, procedure CRF); and
- Successful deployment and correct position of the first intended device (TMVR implant is "Yes", no additional devices opened or used, TMVR device malfunction is "No", and TMVR device failure is "No", procedure CRF); and
- Freedom from emergency surgery or reintervention related to the device or access procedure (Conversion to open MV replacement is "No" and Other repair surgery is "No", procedure CRF).

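### The pilot SAP scores delivery-system retrieval as successful whenever a catheter removal time is recorded, so this component cannot register a failed or incomplete retrieval

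*Combined protocol and SAP*

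**What the plan says.** The first secondary performance endpoint in SAP 7.9.2 has three parts, all taken from the procedure CRF.

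- Access is Yes if a catheter insertion time has been entered.
- Delivery is Yes if the valve is marked as implanted and conversion to open valve replacement is marked No.
- Retrieval has a single condition: the rule that opens "Successful retrieval delivery system is" gives Yes if a catheter removal time has been entered.

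The parts are not combined. The analysis method calls for "The proportion of subjects with each of successful access, successful delivery of implant, and successful retrieval of the delivery system", each with a 95% exact interval, on the Attempted Subjects set. SAP 7.1.3 defines that set as approved subjects who entered the procedure room with intent to attempt TMVR.

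The rule is reused in SAP 7.9.3, where one condition of MVARC technical success reads "Successful access, delivery, and retrieval of the delivery system (same definition as secondary endpoint, procedure CRF". SAP 7.4 says that a subject with missing data is left out of the affected analysis.

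CIP-1403 section 5.2 lists "Failure to retrieve the system components" and embolisation of delivery-system components among the potential risks. Section 2 describes the delivery system as an apical introducer sheath with dilator plus a delivery catheter.

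**The concern.** A timestamp shows that an event was logged. It does not show that the event went well. The retrieval rule asks nothing about whether the catheter came out whole, whether a part was left behind or travelled, whether an unplanned procedure was needed to remove the system, or what became of the sheath. The conversion check belongs to the delivery part and does not reach the retrieval figure, because the three proportions are reported separately.

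The study is descriptive, with no hypothesis tests, and SAP section 5 says that results will be read against historical literature. The reported proportion and its interval are therefore the evidence. A retrieval rate of 100% with a tight exact interval would be read as a performance finding when it reflects only that a time field was filled in.

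**Working it through.** **Step 1: what the rule can and cannot see.** The only input is whether a removal time is present. For the second and third rows, it is an inference that a time would be entered; the procedure CRF is not among the documents.

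| Situation | Removal time | SAP 7.9.2 result | What happened |
|---|---|---|---|
| Catheter and sheath out intact | Recorded | Yes | Success |
| Catheter out, a component retained or embolised | Recorded (inferred) | Yes | Failure |
| System removed by an unplanned procedure | Recorded (inferred) | Yes | Failure |
| Clean removal, time not entered | Blank | Not Yes, or dropped | Success |
| Catheter never inserted | Blank | Not Yes, or dropped | Retrieval not applicable |

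Among the n subjects with a recorded time, the proportion is n/n = 100% by definition.

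**Step 2: is there a stricter definition elsewhere?** The endpoint list in CIP-1403 section 7 names the endpoint without defining it. Appendix D requires successful access, delivery and retrieval but gives no criterion for retrieval. SAP 7.9.3 points back to 7.9.2. No stricter rule exists in the documents.

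**Step 3: what happens to blanks?** The SAP does not say which reading applies.

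- *Blanks are missing data (7.4).* The only value other than Yes leaves the denominator, so the proportion is exactly 100%. The component summary under technical success, which uses non-missing data, behaves in the same way.
- *Blanks count as not Yes.* The proportion falls only with never-inserted catheters and forgotten times. With 95 attempted and 2 never inserted it is 93/95 = 97.9% (92.6 to 99.7), whether or not any retrieval failed.

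**Step 4: illustration of size.** The SAP states no expected retrieval rate, so there is no figure to reproduce. Assume N = 95, the ceiling in SAP section 6, with every catheter inserted and every time recorded. Let s be an assumed number of true retrieval failures. The exact (Clopper-Pearson) limits for x successes in n are the 0.025 quantile of Beta(x, n − x + 1) and the 0.975 quantile of Beta(x + 1, n − x). For x = n the lower limit is 0.025^(1/n) and the upper limit is 1.

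| s | SAP rule | Failures counted, (95 − s)/95 |
|---|---|---|
| 0 | 95/95 = 100% (96.2 to 100) | 95/95 = 100% (96.2 to 100) |
| 2 | 95/95 = 100% (96.2 to 100) | 93/95 = 97.9% (92.6 to 99.7) |
| 5 | 95/95 = 100% (96.2 to 100) | 90/95 = 94.7% (88.1 to 98.3) |
| 10 | 95/95 = 100% (96.2 to 100) | 85/95 = 89.5% (81.5 to 94.8) |

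Each missed failure is worth 1/95 = 1.1 percentage points. The s = 2 result equals the two-never-inserted result in Step 3. Under the second reading of blanks, a figure below 100% therefore cannot be attributed to retrieval either.

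**The case against.** The strongest reply has four parts.

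1. *The form is not available.* Its completion rules might tell sites to leave the time blank after an incomplete removal. This stands as a limit on how often the rule misfires. It does not repair the SAP, which states no such condition.

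2. *The failures are caught elsewhere.* Technical success also requires no additional device opened or used, no device malfunction, no device failure, no conversion and no other repair surgery. Serious related events enter the primary safety endpoint, SAP 7.10 lists adverse events related to the delivery system, and SAP 7.2 provides for individual case review. This largely stands. A reader might infer that technical success is inflated to the same degree, or that a retained component would go unseen; the documents support neither.

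3. *The endpoint is not trivial as a whole.* A reader might infer that all of the access, delivery and retrieval endpoint is close to 100% by construction. It is not: delivery rests on outcome fields, and the Attempted Subjects set can include people in whom no catheter was inserted.

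4. *Conversion is not retrieval failure.* It is tempting to fail every converted subject. CIP-1403 section 4.3 closes the apical access before the implant is evaluated and surgical replacement considered, so in that sequence the system is already out. Access is also surgical by plan, through a mini-thoracotomy, so removal through a surgical opening is not itself a failure. An automatic conversion rule would misclassify clean retrievals and duplicate the delivery component.

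The point is also confined to the transapical pilot. The transseptal protocol names the same endpoint, but no derivation for that study is in the documents, so nothing can be concluded about how it will be scored there.

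**Conclusion.** The point holds for the separately reported retrieval proportion. Among subjects with a recorded time the figure is fixed at 100%, and the proportion cannot register the two retrieval risks that CIP-1403 names. How far the reported figure would be from the truth is unknown: the documents give no retrieval failure count, and the 2, 5 and 10 failures and N = 95 used above are assumptions. The conclusion also assumes that sites enter a removal time after an incomplete or unplanned removal, which is plausible from the field name but unverified.

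The consequence is an uninformative descriptive secondary result. No test, error rate, sample size or pass criterion is affected. The rule should be changed, because the correction is cheap and the component does not measure what its name says.

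**What to change.** Amend SAP 7.9.2 as follows.

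- **Denominator:** Attempted Subjects with a delivery catheter inserted. Report the number never inserted separately; they already fail access.
- **Success:** Yes only if a removal time is recorded and no malfunction or failure entry on the procedure CRF, and no adverse event or CEC record, shows a retained or embolised delivery-system component (sheath included) or an unplanned surgical or interventional procedure to remove the delivery system.
- **Conversion to open surgery:** use it to trigger a check of how the system was removed, not as an automatic failure.
- **Unrecorded time after insertion:** query the site. If it stays unresolved, do not count it as success and do not drop it silently; show it as its own category.
- **Technical success:** apply the same rule in SAP 7.9.3.
- **Reporting:** give the present and revised definitions side by side and document the change as SAP 7.12 requires. SAP 7.8 planned interim analyses at 50 and 75 subjects, the version history describes interim analyses as performed, and it lists no change to the retrieval rule. Results already reported therefore presumably rest on the present definition.

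The cost is some extra derivation work, a possibly lower rate and a break with the interim definition. The malfunction, failure, adverse event and CEC sources are already used in SAP 7.9.3 and 7.10. Whether they record retained components in enough detail cannot be confirmed without the CRF, so some case-level reading may be needed; SAP 7.2 already plans individual review of each subject's data.

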## Data Collection and Analysis Dataset:

Data for this endpoint are collected on the procedure CRF. Data will be summarized on the Attempted Subjects analysis set.

## Analysis Method:

The proportion of subjects with each of successful access, successful delivery of implant, and successful retrieval of the delivery system and its associated 95% exact confidence interval will be calculated.

- Reduction in MR Grade from baseline (measured by echo through 30 days post-procedure)

## Hypothesis/Decision Criteria:

No specific hypotheses or pass/fail criteria have been set. The analysis for each of these endpoints will be descriptive and no statistical hypothesis tests are planned.

## Endpoint Definition/Parameters to Be Estimated:

This endpoint is defined using variables on the core lab echo CRF.

The core lab echo CRF will report 7 grade levels of MR: "None", "Trace", "Mild", "Mild-Moderate", "Moderate", "Moderate-Severe", and "Severe". These will be recategorized to the following 5 grade levels of MR: "None/Trace", "Mild" (Mild + Mild-Moderate), "Moderate", "Moderate Severe", and "Severe", with corresponding numerical values of 0, 1, 2, 3, and 4 respectively. For the post-procedure echo, MR grade is defined as the

highest reported severity level of transvalvular leak and paravalvular leak. MR  $\geq 2+$  is considered as clinically significant. The number of grade level changes since baseline will be calculated. There are 4 possible grade change categories: improved (by 1, 2, 3, or 4 grades), no change, and worsened (by 1, 2, 3, or 4 grades).

#### Data Collection and Analysis Dataset:

Data will be collected on the core lab echo CRF (either TTE or TTE data, whichever demonstrates a higher MR grade, will be used). Analysis dataset is the Implanted Subjects analysis set.

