#### 3.3.2 Exclusion Criteria

The subject may not meet any of the following criteria:

1. Left ventricular ejection fraction (LVEF)  $< 20$
2. Evidence of intracardiac mass, thrombus, or vegetation
3. Pulmonary hypertension ( $> 70$  mmHg systolic)
4. Hypertrophic Obstructive Cardiomyopathy (HOCM)
5. Prior mitral valve surgery or endovascular procedure, any currently implanted mechanical prosthetic valve, or need for other valve surgery/procedure
6. Any endovascular therapeutic interventional or surgical procedure performed within 30 days prior to enrollment
7. Prior stroke within 30 days
8. Need for coronary revascularization
9. Need for emergent surgery
10. History of, or active, endocarditis
11. GI bleeding within 6 months
12. History of bleeding diathesis or coagulopathy or patient will refuse blood transfusion

13. Hemodynamic instability
14. Platelet count of <75,000 cells/mm^3
15. Renal insufficiency (Creatinine > 2.5 mg/dL)
16. Active infections requiring current antibiotic therapy (if temporary illness, patients may enroll 2 weeks after discontinuation of antibiotics)
17. Contraindication to transesophageal echocardiography (TEE)
18. Known hypersensitivity or contraindication to study or procedure medications/contrast which cannot be adequately managed medically.
19. Pregnant, nursing or planning to be pregnant. (Female participants of childbearing potential must have a negative pregnancy test prior to enrollment).

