## 4.1 Screening/Baseline

Standard examinations and tests, which are typically performed for patients undergoing similar procedures such as conventional mitral valve surgery, minimally invasive mitral valve repair (e.g., MitraClip), or Transcatheter Aortic Valve Implantation (TAVI) will be used both to screen eligible patients and provide baseline information for those patients that meet study criteria. These tests include:

- Demographic information and medical history including risk factors
- Physical examination including vital signs, height and weight, and NYHA Class
- Transthoracic Echocardiogram (TTE)
- Transesophageal Echocardiography (TEE)
- Cardiac Computed Tomography (CT)
- Coronary angiography
- Electrocardiogram (ECG)
- Blood tests
  - Chemistry profile including creatinine
  - CK, CKMB
  - Complete Blood Count
  - Coagulation panel
  - Urinalysis
  - Plasma free hemoglobin
- Pregnancy test (urine or blood) if female of child-bearing age
- 6-minute walk test (6MWT)
- Quality of Life (QOL) survey – Minnesota Living with Heart Failure Questionnaire

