## 4.6 Post-Procedure Follow-Up

The following standard exams and tests will be performed at 1, 3, 6 months ( $\pm$  2 weeks), at 12 months and every 6 months ( $\pm$  30 days) through 5 years:

- Physical exam (including NYHA Class) and review of adverse events
- 6 minute walk test (6MWT)
- TTE and/or TEE evaluation
- ECG
- Blood tests
  - Chemistry profile including creatinine
  - CK, CKMB
  - Complete Blood Count
  - Coagulation panel
  - Urinalysis
  - Plasma free hemoglobin

In addition, at 12 months only, the following will be performed:

- Cardiac Computed Tomography (CT)
- QOL survey – Minnesota Living with Heart Failure Questionnaire

*Note:* If a subject's TMVR implant is replaced with surgical replacement valve, the subject will be followed through 1 month post-surgical replacement.

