## Appendix A: Schedule of Visits and Procedures

Test / Evaluation	Baseline	Implant Procedure	Discharge	1, 3, 6M (± 2 wks)	12M (± 30 days)	Every 6M (± 30 days) through 5 yrs
Informed Consent	X					
Medical History	X					
Physical Exam (including NYHA Class)	X		X	X	X	X
6-minute walk test	X			X	X	X
Blood Tests: Chemistries (incl. creatinine), CBC, CK/CK-MB, Coagulation panel, plasma free hemoglobin	X	X	X	X	X	X
Pregnancy Test (blood or urine), if appropriate	X					
ECG (12 lead)	X	X	X	X	X	X
Coronary angiogram	X					
Transthoracic Echocardiography (TTE)	X		X 	X 	X 	X 
Transesophageal Echocardiography (TEE)	X	X	X 	X 	X 	X 
Cardiac Computed Tomography (CT)	X		X		X	
Hemodynamics		X				
Quality of Life (QOL) Survey	X				X	
Adverse Events	X	X	X	X	X	X

 TTE or TEE per physician discretion

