## 1. Version History

Version	Summary of Changes	Author(s)/Title
1.0	

Not Applicable, New Document

	[name], Sr Prin Statistician
2.0	

Updated throughout to align with the current version of the CIP.

Added ISO 14155:2020 requirements per the current Statistical Analysis Plan Template B.

Section 7.8: Added description of the interim analyses performed.

Section 7.1.3: Added the analysis sets for consented subjects and approved subjects. Removed the per protocol and modified per protocol analysis datasets, since there were no previous analyses performed or future analyses planned for these populations.

Section 7.9.3: Added the MVARC criteria for technical, procedural, device and patient success per FDA request.

	[name], Senior Statistician
3.0	

Includes language to exclude echocardiography data after explant of the study valve from analysis.

Clarified greater severity between TTE and TEE will be reported where applicable.

Minor formatting updates and update to SAP template version C.

	[name], Senior Statistician
4.0	

Updated definition of LVOT Patency to align with current Mitral study definitions.

Included an additional contemporary definition for Mitral Valve Stenosis.

Updated French CIP protocol number and date, and formatted Australian CIP version date.

Added "Mild-Moderate" and "Moderate-Severe" as mitral regurgitation levels, and updated categorization.

Updated proportion confidence interval descriptions to exact confidence intervals

Added additional options for device relatedness to adverse event to align with current CEC charter.

	[name], Senior Statistician

Version	Summary of Changes	Author(s)/Title
	

• Refined MVARC composite endpoint denominators to denote inclusion of subjects with any failures.

• Replaced Approved with Attempted for the Analysis cohorts in various outcomes.

• Updated the method for Kaplan-Meier standard errors to be Greenwood throughout.

• Minor formatting updates.

	

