#### Analysis Method:

Number and percentage of subjects with no significant MV stenosis at each visit will be calculated as appropriate by definition. Statistics summarizing the distributions of the component endpoints (number and percentage of subjects with MV mean gradient  $\leq 5$  mmHg and  $< 10$  mmHg, number and percentage of subjects with EOA  $\geq 1.5$  cm $^2$ ) will also be presented.

- LVOT patency (measured by echo through 30 days post-procedure)

Hypothesis/Decision Criteria:

No specific hypotheses or pass/fail criteria have been set. The analysis will be descriptive and no statistical hypothesis tests are planned.

Endpoint Definition/Parameters to Be Estimated:

This endpoint is defined using variables on the core lab echo CRF.

LVOT patency is defined as not having an LVOT obstruction. LVOT obstruction is defined as having peak LVOT jet velocity  $\geq 2.7$  m/s (peak instantaneous gradient  $\geq 30$  mmHg) measured by CW Doppler under basal (resting) conditions or physiologically provoked (Valsalva maneuver or post premature ventricular contraction) and having an increment in peak LVOT gradient  $\geq 10$  mmHg from baseline.

Data Collection and Analysis Dataset:

Data will be collected on the core lab echo CRF (either TTE or TTE data, whichever demonstrates a higher degree of LVOT obstruction (equivalent to lowest degree of patency), will be used). Analysis dataset is the Implanted Subjects analysis set.

Analysis Method:

Number and percentage of subjects with LVOT patency at each visit will be calculated. Statistics summarizing the distributions of the component endpoints (number and percentage of subjects with peak instantaneous gradient  $\geq 30$  mmHg, and number and percentage of subjects with an increment in peak LVOT gradient  $\geq 10$  mmHg from baseline) will also be presented.

- Improvement of NYHA Class from baseline (through 30 days post-procedure)

Hypothesis/Decision Criteria:

No specific hypotheses or pass/fail criteria have been set. The analysis will be descriptive and no statistical hypothesis tests are planned.

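### As written, SAP 7.9.2 can set a worst-of-two baseline MR grade against a single-exam follow-up grade, which tilts MR-grade change modestly toward improvement

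*Combined protocol and SAP*

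**What the plan says.** The SAP in the file is the one for the pilot study (CIP-1403), so the pilot protocol is the one to read beside it.

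- **Selection rule.** SAP 7.9.2, on reduction in MR grade, says of the core-lab echo data: "either TTE or TTE data, whichever demonstrates a higher MR grade, will be used". The printed text names TTE twice. The version 3.0 entry in the SAP's Version History shows the intent: "Clarified greater severity between TTE and TEE will be reported where applicable". No time points are named. By contrast, the endpoint definition just before it expressly confines the maximum of transvalvular and paravalvular leak to the post-procedure echo.
- **Change from baseline.** The same endpoint states: "The number of grade level changes since baseline will be calculated". The analysis uses subjects with paired data and does not match on modality. Section 7.9.3 carries this through 5 years.
- **Baseline exams.** Pilot protocol 4.1 lists TTE and TEE as separate tests that "will be used both to screen eligible patients and provide baseline information for those patients that meet study criteria". Appendix A marks both at baseline without a footnote. Section 3.3.2 excludes patients with "Contraindication to transesophageal echocardiography (TEE").
- **Follow-up exams.** Sections 4.5 and 4.6 ask for "TTE and/or TEE evaluation". The Appendix A footnote, from discharge to 5 years, reads "TTE or TEE per physician discretion".
- **LVOT.** SAP 7.9.2 selects the exam "whichever demonstrates a higher degree of LVOT obstruction (equivalent to lowest degree of patency), will be used". Obstruction needs a peak gradient of at least 30 mmHg and also a rise of at least 10 mmHg from baseline.

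**The concern.** A worst-exam rule is conservative for a post-procedure value, because it reports the poorer result. For a baseline reference it works the other way: it raises the starting point and so enlarges the apparent reduction. If the rule acts on two exams at baseline and one at follow-up, part of the reported reduction reflects how many exams each visit had.

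The study has a single arm, and SAP section 5 says the results will be read against historical literature, so no control group cancels such a shift. SAP 7.8 plans interim analyses for publication and for a CE submission. The affected outputs are the MR-grade change categories, their 5-year versions, and the part of the LVOT endpoint that uses a rise from baseline.

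**Working it through.** The plan states no figure for this point, so there is nothing to reproduce. The check covers direction, then size.

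**1. Direction.** Let B_TTE and B_TEE be the two baseline grades and F_m the follow-up grade from the single modality m.

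- Change under the SAP rule: max(B_TTE, B_TEE) − F_m
- Change with matched modality: B_m − F_m
- Difference: max(B_TTE, B_TEE) − B_m, which is never negative

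The follow-up grade cancels. The leak maximum sits inside F_m, so it does not remove the asymmetry. Where both exams are done at follow-up, both sides are worst-of-two and the asymmetry is gone.

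**2. Hand calculation.** Entry requires 3+ or 4+ (pilot protocol 3.3.1). Assume a 50:50 true mix, with each exam misreading 3 as 4 or 4 as 3 with probability p, independently. One exam grades 50% of subjects 4+. The worse of two grades

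0.5[1 − (1 − p)²] + 0.5[1 − p²] = 0.5 + p(1 − p)

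as 4+. That is 59%, 66% and 71% at p = 0.10, 0.20 and 0.30, a mean excess of 0.09, 0.16 and 0.21 grade. Independence makes these high, since both exams view the same valve.

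**3. Simulation allowing correlation.** 400,000 subjects per scenario on the SAP's 0–4 scale. All inputs are assumptions: true baseline 40% grade 3 and 60% grade 4; low residual leak; reading-error SD 0.3, 0.5 or 0.8 grade; TTE/TEE error correlation 0, 0.5 or 0.9. Excess mean reduction under the SAP rule, in grades:

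| Exams at follow-up | Versus TTE at both times | Versus worst-of-two at both times |
|---|---|---|
| One for every subject | 0.02 to 0.30 | 0.03 to 0.33 |
| Both for half | 0.01 to 0.14 | 0.02 to 0.16 |
| Both for all | no excess | 0.00 |

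At SD 0.8 with one follow-up exam, the excess over TTE-to-TTE falls from 0.30 to 0.21 to 0.10 as the correlation rises from 0 to 0.5 to 0.9. If TEE is assumed to read 0.5 grade lower than TTE, the excess is 0.01 to 0.10. If entry requires a TTE grade of at least 3, it is 0.04 to 0.14 (both at correlation 0.5).

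Where it lands, with one follow-up exam:

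| Scenario | Output | SAP rule | TTE to TTE | Difference |
|---|---|---|---|---|
| SD 0.5, corr. 0.5 | Mean reduction | 3.13 | 2.99 | 0.14 |
| SD 0.5, corr. 0.5 | Improved ≥3 grades | 79.7% | 73.8% | 5.9 points |
| SD 0.5, corr. 0.5 | Improved ≥1 grade | 99.7% | 99.4% | 0.3 points |
| SD 0.8, corr. 0 | Improved ≥3 grades | 74.5% | 62.0% | 12.5 points |
| SD 0.8, corr. 0 | Improved ≥1 grade | 99.1% | 97.2% | 1.9 points |

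Exam count also matters within a visit: in the SD 0.5, correlation 0.5 case, follow-up MR of 2+ or more is 6.0% with one exam and 8.8% with two.

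**4. LVOT.** Obstruction needs G_post ≥ 30 and G_post − G_base ≥ 10. With G_post ≥ 30, the second condition fails only if G_base > G_post − 10, hence only if G_base > 20 mmHg. If each exam's gradient error is independent with an assumed SD of 3 to 6 mmHg, the worse of two raises baseline on average by 0.564 × SD, or 1.7 to 3.4 mmHg. For that average rise to cross 20, the underlying baseline must already exceed 20 − 3.4 = 16.6 to 20 − 1.7 = 18.3 mmHg. A baseline of 5 raised to 8.4, with 30 afterwards, still shows a rise of 21.6 and is still called obstruction.

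**The case against.** **The rule may not be meant for baseline.** No time points are named, and the version log adds a where-applicable qualifier. This stands as a limit: that the rule governs every time point is an inference from unrestricted wording. It does not dispose of the point, because the same endpoint restricts its leak rule to post-procedure echoes and leaves this one open.

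**Single-exam follow-up is permitted, not shown to be usual.** A reader might infer from the Appendix A footnote that follow-up normally has one exam. Sections 4.5 and 4.6 allow both, and nothing says how often both are done. TEE ordered for a suspected leak would shrink the shift. This stands.

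**Only the US schedule is available.** The SAP covers seven geographies, and the other protocols are not in the file. This stands.

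**LVOT patency.** A reader might infer that patency is biased in the same way. The documents do not support that: the 30 mmHg condition protects the call unless the baseline used exceeds 20 mmHg, no baseline gradients are given, and hypertrophic obstructive cardiomyopathy is excluded. The selection rule also has no clear meaning at baseline, since obstruction is itself defined by a rise from baseline. What stays exposed is mainly the separately reported increment component.

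**Nothing is decided by it.** There are no tests or pass criteria, and the MR distribution at each visit is reported regardless. This is correct and limits the weight of the point, but the number of grades improved is still a planned output.

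**TTE at both times is not a safe remedy.** Where both follow-up exams were done and TEE was worse, it would drop the worse result, which favours the device. The fix below avoids this.

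**Conclusion.** The point holds for MR-grade change. As written, the SAP compares a worst-of-two baseline with a follow-up grade that may rest on one exam, and at such visits the rule can only enlarge the reduction or leave it unchanged.

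The direction follows from the text, provided the rule covers baseline. The size does not: 0.02 to 0.30 grade against TTE-to-TTE rests wholly on assumed error sizes and correlations, and it shrinks toward zero as more follow-ups have both exams. The effect falls mainly on how many grades subjects improved. Any improvement moves by about 2 points at most. The requirement in acceptable device success for a reduction of at least 1 grade is hardly affected: that definition also requires post-procedure MR of 1+ to 2+, and a 3+ baseline against 2+ already gives 3 − 2 = 1.

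A reader might conclude that the performance endpoints are invalid or that an error rate is inflated. Neither follows from a small shift in a descriptive analysis with no hypothesis test. The wording should still be changed, because the remedy is cheap.

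**What to change.** In SAP 7.9.2, and so in 7.9.3 by reference:

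1. Correct the typing error so that the rule names TTE and TEE; it recurs under MV stenosis and LVOT patency.
2. For change in MR grade and for the LVOT increment, take the baseline value from the modality or modalities available at that follow-up visit: baseline TTE if only TTE was done, baseline TEE if only TEE was done, and the worse of two at both times if both were done.
3. Keep the greater-severity rule for the by-visit post-procedure summaries.
4. Report how many subjects had TTE only, TEE only or both at each visit.

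The cost is SAP wording and some reprogramming of core-lab echo data, with no new patient data. Reported reductions may be slightly smaller. A subject's baseline can differ between visits, which needs a table footnote, and subjects without a matched pair would be listed separately.
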